
Other Secondary^b
 
To assess whether mirikizumab induction dosing is superior to placebo with respect to an early, clinically meaningful response
 
To compare mirikizumab to placebo with respect to clinical response and time to clinical response during the induction dosing period, and with respect to patient-reported outcomes during the induction dosing period
	
At Week 4:
 
 • Proportion of patients achieving PASI 75 
At Week 16 and various time points over the first 16 weeks of dosing:
 
 • Proportion of patients achieving PASI 90 • Change from baseline in PPASI total score in patients with palmoplantar involvement at baseline • Change in PSSI total score in patients with scalp involvement at baseline • Change from baseline in NAPSI total score in patients with fingernail involvement at baseline • Change from baseline on the SF-36 physical component summary (PCS) and mental component summary (MCS) • Change from baseline on PatGA of disease severity** • Change from baseline for the WPAI PSO scores (Absenteeism, Presenteeism, Work Productivity Loss, and Activity Impairment) • Change from baseline in QIDS-SR16 total score in those with a baseline QIDS-SR16 total score ≥ 11 • Proportion of patients achieving a DLQI total score of (0,1) with at least a 5-point improvement (reduction) from baseline in patients with a baseline DLQI total score ≥ 5 • Proportion of patients achieving DLQI (0,1) with DLQI baseline score > 1

Protocol-Defined Objectives and Endpoints

Objectives	Endpoints

To compare mirikizumab to secukinumab with respect to clinical response and time to clinical response during the induction dosing period, and with respect to patient-reported outcomes during the induction dosing period
 
To assess whether 250-mg mirikizumab Q8W and 125-mg mirikizumab Q8W maintenance dosing is noninferior to secukinumab with respect to high levels of clinical response
	
At Week 16 and various time points over the first 16 weeks of dosing:
 
 • Proportion of patients achieving PASI 90 
At Week 24:
 
 • Proportion of patients achieving PASI 90 
At Week 52:
 
 • Proportion of patients achieving an sPGA (0)

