6.1.1. Patient Populations for Analysis

Patient populations are defined in [Table AMAJ.6.1](#) along with the analysis they will be used to conduct. Patients will be analyzed according to the treatment to which they were assigned for all populations. [Table AMAJ.6.2](#) describes the treatment groups and the comparisons for each study period and the analysis population.

Table AMAJ.6.1. Patient Populations for Analysis

Population	Description
All Entered Patients	All patients who signed informed consent.
Intent-to-Treat (ITT) Population	All randomized patients, even if the patient does not take the assigned treatment, does not receive the correct treatment, or otherwise does not follow the protocol. Unless otherwise noted, efficacy and health outcomes analyses for the both induction period and combined induction/maintenance periods will be conducted on this population.
Induction Safety	All randomized patients who received at least 1 dose of study treatment . Safety analyses for the induction period will be conducted on this population.
All Active Treatment Safety	All randomized patients who received at least 1 dose of mirikizumab or secukinumab .
Induction PPS	All randomized patients who do not have important protocol deviations excluded from per protocol analysis (IPDPP) in the induction period. IPDPP are described in a separate document referred to as the “The AMAJ Trial Issues Management Plan”. These patients will be used to reanalyze the primary endpoints only.
Induction and Maintenance PPS	All randomized patients who do not have IPDPP in the combined induction/maintenance periods. IPDPP are described in a separate document referred to as the “The AMAJ Trial Issues Management Plan.” These patients will be used to reanalyze the selected major secondary endpoints of PASI 90 and sPGA (0,1) at Week 52.

Abbreviations: PASI = Psoriasis Area and Severity Index; PASI 90 = $\geq 90\%$ improvement in PASI from baseline; PPS = per protocol set; sPGA = static Physician’s Global Assessment.

Table AMAJ.6.2. Treatment Groups and Comparisons for Each Study Period and Analysis Population

Study Period	Analysis Population	Treatment Groups	Inferential Comparisons
Induction Period	ITT; Induction Safety; Induction PPS	placebo Q4W; 300 secu; 250 miri Q4W	300 secu vs placebo Q4W; 250 miri Q4W vs placebo Q4W; 250 miri Q4W vs 300 secu

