Baseline sPGA score	No	Moderate (3), Severe (4), or Very severe (5)	X	X
Baseline BSA (%)	Yes	<20%, ≥20%	X	X
Baseline PSSI	Yes	None		
Baseline NAPI	Yes	None		
Baseline PPASI	Yes	None		

Patient Characteristics (and Variables for Subgroup Analysis)

Variable	Quantitative Summary	Categorical Summary	Subgroup Analysis ^a	
			Week 16	Week 52
Baseline Disease Severity				
Baseline PSS sign scores	Yes	0, >0 to <1, ≥1		
Baseline PSS symptom score	Yes	0, >0 to <1, ≥1		
Baseline PatGA	No	0 (Clear), 1, 2, 3, 4, 5 (Severe)		
Baseline DLQI total score	Yes	0 or 1, >1		
		≤10, >10		
		<5, ≥5		
Baseline SF-36 PCS	Yes	None		
Baseline SF-36 MCS	Yes	None		
Baseline WPAI-PSO employment status	No	Yes, No		
Baseline WPAI-PSO score	Yes	None		
Baseline QIDS-SR16 score	Yes	<11, ≥11	X	X
		None (0-5), Mild (6-10), Moderate (11-15), Severe (16-20), Very severe (21-27)		

Abbreviations: BMI = body mass index; BSA = body surface area; DLQI = Dermatology Life Quality Index; eCRF = electronic case report form; IL-17 = interleukin 17; MCS = Mental Component Summary; NAPSI = Nail Psoriasis Severity Index; PASI = Psoriasis Area and Severity Index; PatGA = Patient's Global Assessment of Psoriasis; PCS = Physical Component Summary; PPASI = Palmoplantar Psoriasis Severity Index; PSS = Psoriasis Symptoms Scale; PSSI = Psoriasis Scalp Severity Index; QIDS-SR16 = 16-item Quick Inventory of Depressive Symptomatology; SF-36 = Short Form 36-item Health Survey; sPGA = static Physician's Global Assessment; TNF = tumor necrosis factor; WPAI-PSO = Work Productivity Activity Impairment Questionnaire – Psoriasis.

- a Subgroup analysis will be used for efficacy endpoints only. See Section 6.15.1 for more details.
- b Age in years will be calculated as length of the time interval from the imputed date of birth (July 1st in the year of birth collected in the eCRF) to the date that the patient was randomized.
- c BMI will be calculated as: $BMI (kg / m^2) = Weight (kg) / (Height (m))^2$.
- d Biologic systemic therapies include: Efalizumab, Ustekinumab, Infliximab, Etanercept, Alefacept, Adalimumab, Golimumab, Certolizumab pegol, Secukinumab, Ixekizumab, Brodalumab and other biologic agent.
- e Nonbiologic systemic therapies include: Cyclosporine, Methotrexate, Corticosteroids, Acitretin, Fumaric acid derivatives, Apremilast other systemic agent, and psoralen and ultraviolet A (PUVA).
- f Anti-TNF alpha biologics include: Infliximab, Etanercept, Adalimumab, Golimumab, and Certolizumab pegol.

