		DLQI daily activities domain	Sum of responses of questions #3 and #4: #3. How much has your skin interfered with you going shopping or looking after your home or garden? #4. How much has your skin influenced the clothes you wear?	If 1 question in a domain is missing, that domain is missing.
		DLQI leisure domain	Sum of responses of questions #5 and #6: #5. How much has your skin affected any social or leisure activities? #6. How much has your skin make it difficult for you to do any sport?	If 1 question in a domain is missing, that domain is missing.
		DLQI work and school domain	Sum of responses of questions question #7A and #7B: #7A. Has your skin prevented you from working or studying? #7B. If No: how much has your skin been a problem at work or studying?	If the answer to question #7A is missing, this domain is missing. If #7A is No, and #7B is missing, this domain is missing.
		DLQI personal relationships domain	Sum of responses of questions #8 and #9: #8. How much has your skin created problems with your partner or any of your close friends or relatives? #9. How much has your skin caused any sexual difficulties?	If 1 question in a domain is missing, that domain is missing.
		DLQI treatment domain	Response of question #10: #10. How much of a problem has the treatment for your skin been, for example by making your home messy, or by taking up time?	If 1 question in a domain is missing, that domain is missing.
WPAI-PSO	The Work Productivity and Activity Impairment-Psoriasis (WPAI-PSO) Questionnaire is a patient-reported instrument developed to measure the	Employment Status	Yes/No	Missing if question is missing
		Absenteeism Score (%)	$\frac{Q2}{(Q2 + Q4)} \times 100$	Missing if Q2 or Q4 are missing. Also missing if

Measure	Description	Variable	Derivation/Comment	Imputation Approach if with Missing Components
	impact on work productivity and regular activities attributable to a specific health problem (psoriasis). It contains 6 items that measure: 1) employment for pay status, 2) hours missed from work due to the psoriasis, 3) hours missed from work for other reasons, 4) hours actually worked, 5) degree of health-affected productivity while working, and 6) degree of health affected productivity in regular unpaid activities. Greater scores indicate greater impairment (Reilly Associates Health Outcomes Research [WWW]).			Employment Status is No.

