		Presenteeism Score (%)	$\frac{Q5}{10} \times 100$	Missing if Q5 is missing. Also missing if Employment Status is No.
		Work Productivity Loss Score (%)	$\left[\frac{Q2}{Q2 + Q4} + \left(1 - \frac{Q2}{Q2 + Q4} \right) \frac{Q5}{10} \right] \times 100$	Missing if Q2, Q4, or Q5 is missing. Also missing if Employment Status is No.
		Activity Impairment Score (%)	$\frac{Q6}{10} \times 100$	Missing if Q6 is missing. May still be present and nonmissing if patient is unemployed.
SF-36	The SF-36 Version 2 is a 36-item, patient-completed measure designed to be a short, multipurpose assessment of health (The SF Community – SF-36 Health Survey Update). The summary scores range from 0-100, with higher scores indicating better levels of function and/or better health. Items are answered on Likert scales of varying lengths. The SF-36 comprises 8 domain scores and 2 overarching component scores. SF-36 domain scores are: (1) Physical functioning, (2) Role-physical, (3) Role-emotional, (4) bodily pain, (5) vitality, (6) social functioning, (7) mental health, and (8) general health. The component scores are: (1) the Physical Component Summary (PCS) and (2) Mental Component Summary (MCS).	SF-36 Domain scores and SF-36 Component Scores	Per copyright owner, the Quality Metric Health Outcomes™ Scoring Software will be used to derive SF-36 domain and component scores. After data quality-controls, the SF-36 software will recalibrate the item-level responses for calculation of the domain and component scores. These raw scores will be transformed into the domain scores (t-scores) using the 1-week recall period. This entails exporting the patient data in a CSV or tab-delimited file for import, generation of the SF-36 scores and reports, and export of the calculated scores in a CSV or tab-delimited file for integration into SDTM/ADAM datasets.	Missing data handling offered by SF-36 software will be used. “Maximum Data Recovery” will be selected for Missing Score Estimator in the software.
		SF-36 change from baseline for domain and component	Calculated as: observed SF-36 score – baseline SF-36 score	Missing if baseline or observed value is missing

Measure	Description	Variable	Derivation/Comment	Imputation Approach if with Missing Components
	The SF-36 acute version will be used, which has a 1 week recall period. Responder Definitions were determined in the user's manual (Maruish 2011).	scores		

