	DLQI (0,1)	CMH analysis with NRI	ITT - Patients with Baseline DLQI > 1	All scheduled visits in Induction Period; All scheduled visits in Induction and Maintenance Periods
	DLQI total score ≥ 5 -point reduction from baseline	CMH analysis with NRI	ITT - Patients with Baseline DLQI ≥ 5	All scheduled visits in Induction Period; All scheduled visits in Induction and Maintenance Periods
	DLQI total score and domain scores change from baseline	MMRM; ANCOVA with mBOCF	ITT	All scheduled visits in Induction Period; All scheduled visits in Induction and Maintenance Periods
SF-36	SF-36 change from baseline for PCS and MCS Component Scores and Domain Scores	ANCOVA with mBOCF	ITT	Last visit in Induction Period
		MMRM; ANCOVA with mBOCF	ITT	All scheduled visits in Induction and Maintenance Periods
	SF-36 PCS Responder Definition; SF-36 MCS Responder Definition; SF-36 Domain score Responder Definition;	CMH analysis with NRI	ITT	Last visit in Induction Period; All scheduled visits in Induction and Maintenance Periods
PatGA	PatGA(0)	CMH analysis with NRI	ITT - Patients with Baseline PatGA > 0	All scheduled visits in Induction Period; All scheduled visits in Induction and Maintenance Periods
	PatGA (0,1) and ≥ 2 -point improvement from baseline	CMH analysis with NRI	ITT - Patients with Baseline PatGA ≥ 2	All scheduled visits in Induction Period; All scheduled visits in Induction and Maintenance Periods
WPAI-PSO	Change from baseline in WPAI-PSO Scores (Absenteeism, Presenteeism, Work Productivity, Activity Impairment)	ANCOVA with mBOCF	ITT - Patients with Baseline Employment Status of Yes	Last visit in Induction Period
		MMRM; ANCOVA with mBOCF	ITT - Patients with Baseline Employment Status of Yes	All scheduled visits in Induction and Maintenance Periods

Description of Efficacy/Health Outcomes Analyses

Measure	Variable	Analysis Method (Section 6.1.2)	Population (Section 6.1.1)	Time Point and Period
TSQM	Mean Effectiveness, Convenience, and Global Satisfaction	ANCOVA with mBOCF	ITT	Last visit in Induction Period
		MMRM; ANCOVA with mBOCF	ITT	All scheduled visits in Induction and Maintenance Periods
EQ-5D-5L + Bolt On	Change from baseline of EQ-5D VAS and Index scores	MMRM; ANCOVA with mBOCF	ITT	All scheduled visits in Induction Period; All scheduled visits in Induction and Maintenance Periods
	EQ-5D Dimension Scores with no problems	CMH analysis with NRI	ITT	All scheduled visits in Induction Period; All scheduled visits in Induction and Maintenance Periods

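### The WPAI-PSO Activity Impairment score is analysed only in patients employed at baseline, although the SAP derives it for patients without paid work and gives no reason for excluding them

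*SAP*

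**What the plan says.** **Analysis population.** In SAP Section 6.11, Table AMAJ.6.6 has one WPAI-PSO entry that names Absenteeism, Presenteeism, Work Productivity and Activity Impairment together. It has two method lines: ANCOVA with mBOCF at the last induction visit, and MMRM plus ANCOVA with mBOCF over the combined Induction and Maintenance Periods. Both give the population as "ITT - Patients with Baseline Employment Status of Yes".

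**Derivation.** Table AMAJ.6.5 treats the four scores differently. For Presenteeism the missing-data rule is "Missing if Q5 is missing. Also missing if Employment Status is No", and Absenteeism and Work Productivity Loss carry the same employment condition. Activity Impairment is item 6 divided by 10 and multiplied by 100. It is missing only when item 6 is missing, and the table adds "May still be present and nonmissing if patient is unemployed". The table describes item 6 as the "degree of health affected productivity in regular unpaid activities".

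**Default.** Table AMAJ.6.1 says of the ITT population: "Unless otherwise noted, efficacy and health outcomes analyses for the both induction period and combined induction/maintenance periods will be conducted on this population".

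**Endpoint.** Table AMAJ.4.1 lists change in all four WPAI-PSO scores as an Other Secondary endpoint, with no employment condition. Other endpoints in the same list do state their baseline subsets, for example scalp involvement or a QIDS-SR16 total of at least 11.

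**The concern.** The SAP defines a valid Activity Impairment score for patients without paid work and then leaves those patients out of its only planned analysis. The employment condition appears to have been applied to the whole instrument when only three of its four scores need it.

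SAP Section 4 names Table AMAJ.6.6 as one of the places that define the population of interest for each estimand. As written, the Activity Impairment result therefore describes employed patients only, whereas the protocol-defined endpoint carries no such limit.

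Two things are at stake: precision, because usable observations are dropped, and coverage, because people such as retirees, homemakers, students and the unemployed have no result on the one WPAI-PSO score that can be computed for them. Validity of the randomised comparison is not at stake, because the subset is defined by a baseline characteristic.

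**Working it through.** The documents state no sample size, power or employment rate for WPAI-PSO, so there is no planned figure to reproduce. The check is a comparison of the tables, followed by an illustration of size.

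**1. Does the restriction fit each score?**

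| Score | Source items | Set to missing if not employed (Table AMAJ.6.5) | Restricted to employed at baseline (Table AMAJ.6.6) | Fits? |
|---|---|---|---|---|
| Absenteeism | 2, 4 | Yes | Yes | Yes |
| Presenteeism | 5 | Yes | Yes | Yes |
| Work Productivity Loss | 2, 4, 5 | Yes | Yes | Yes |
| Activity Impairment | 6 | No | Yes | No |

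**2. Is the excluded group picked up elsewhere?** No other row of Table AMAJ.6.6 covers Activity Impairment, and Section 6.12 only refers back to the two tables. By contrast, "DLQI total score and domain scores change from baseline" is analysed in unrestricted ITT, as are SF-36 and EQ-5D changes.

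**3. Is the restriction signalled as deliberate?** Footnotes to Table AMAJ.4.1 mark two places where the protocol wording should be updated; neither concerns WPAI-PSO. The revision history in Section 3 mentions no change to this population. The PSS row of Table AMAJ.6.6 shows that one row can assign different populations to different scores, but the WPAI-PSO row does not do so.

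**4. Size.** Inputs from SAP Section 5.2: 888 mirikizumab (two arms of 444), 444 secukinumab and 111 placebo, total 1443. Table AMAJ.6.4 plans to summarise "Baseline WPAI-PSO employment status" but gives no rate. Let *f* be the fraction employed at baseline; the values 0.8, 0.7 and 0.6 are assumptions.

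- Patients left out = 1443 × (1 − *f*).
- The standard error of a difference is σ√(1/n₁ + 1/n₂). If both groups shrink by *f* and variances are equal, it grows by 1/√*f*.

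| *f* | Left out | Week 16, mirikizumab vs placebo | Week 52, each mirikizumab arm vs secukinumab | SE ratio |
|---|---|---|---|---|
| 1 (full ITT) | 0 | 888 vs 111 | 444 vs 444 | 1 |
| 0.8 | 1443 × 0.2 = 289 | 710 vs 89 | 355 vs 355 | 1/√0.8 = 1.118 |
| 0.7 | 1443 × 0.3 = 433 | 622 vs 78 | 311 vs 311 | 1/√0.7 = 1.195 |
| 0.6 | 1443 × 0.4 = 577 | 533 vs 67 | 266 vs 266 | 1/√0.6 = 1.291 |

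**5. Allowing for incomplete item 6.** Let *c* be the share of non-employed patients with a baseline item 6 value, with all employed patients having one. Then patients left out = 1443 × (1 − *f*) × *c*, and SE ratio = √[(*f* + (1 − *f*)*c*)/*f*]. With *c* = 0.8 (assumed):

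- *f* = 0.8: 1443 × 0.2 × 0.8 = 231; √(0.96/0.8) = 1.095.
- *f* = 0.7: 1443 × 0.3 × 0.8 = 346; √(0.94/0.7) = 1.159.
- *f* = 0.6: 1443 × 0.4 × 0.8 = 462; √(0.92/0.6) = 1.238.

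If item 6 is equally complete in employed and non-employed patients, the ratio returns to 1/√*f*.

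**The case against.** **The tables do not contradict each other.** One derives scores and the other sets populations. The ITT default yields where a row says otherwise, and this row does. The note about unemployed patients also has a use under the restriction, because someone employed at baseline who later stops work keeps an Activity Impairment score. All of this is correct, so the plan can be executed as written. It does not explain why a patient who leaves work after baseline stays in while one with a valid item 6 answer who was never in work is left out.

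**A single population lets the four scores be read on the same patients.** This is a reasonable motive, but the SAP does not state it.

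**The reason may be in the main protocol.** The protocol document supplied is the Japan addendum only, so this cannot be excluded. The finding that no reason is given applies to the documents at hand. The protocol-defined endpoint reproduced in Table AMAJ.4.1 carries no restriction.

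**The size rests on assumed rates.** This stands. With 10% not employed, about 144 patients are left out and the standard error is 5% larger (1/√0.9 = 1.054). With *c* = 0.8 as well, the figures are about 115 patients and 4% (√(0.98/0.9) = 1.043).

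**The consequence is small.** This also stands. The SAP permits additional exploratory analyses, so a full-ITT result could still be produced, but it would not be prespecified here.

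**Conclusion.** The concern holds. Table AMAJ.6.6 applies an employment restriction to a score whose derivation does not require employment, no reason is given in the documents supplied, and no other analysis restores the excluded patients.

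The text comparison is certain; the size is not. Assuming 20% to 40% of patients are not employed at baseline, with baseline item 6 available in 80% to 100% of them, roughly 231 to 577 patients are dropped and the standard error is 10% to 29% larger. A lower non-employment rate would make the loss smaller.

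The effect is confined to precision and coverage for one of four scores in an Other Secondary endpoint. That endpoint lies outside the graphical testing procedure of SAP Section 6.5, so type I error control and the primary and major secondary conclusions are unaffected. The change is worth making because it recovers usable data at almost no cost.

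**What to change.** Split the WPAI-PSO entry in Table AMAJ.6.6 in two:

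- **Absenteeism, Presenteeism and Work Productivity Loss:** keep the population of patients employed at baseline.
- **Activity Impairment:** all ITT patients with a baseline item 6 value, with the methods and time points that the table already gives.

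If the restriction is intended for Activity Impairment, state the reason in the SAP and add the full-ITT result as a supportive analysis.

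The cost is one extra table row and its outputs. The three work-score analyses do not change. No new data collection is needed, provided that item 6 was collected from non-employed patients, as the derivation note implies.

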6.11.1. Primary Outcome and Methodology

Primary outcome PASI 90 and sPGA (0,1) and their analysis are described in [Table AMAJ.6.5](#) and [Table AMAJ.6.6](#).

6.11.2. Major Secondary Efficacy Analyses

Major secondary outcomes and their analyses are described in [Table AMAJ.6.5](#) and [Table AMAJ.6.6](#).

6.11.3. Other Secondary Efficacy Analyses

Other secondary outcomes and their analyses are described in [Table AMAJ.6.5](#) and [Table AMAJ.6.6](#).

6.11.4. Sensitivity Analyses

Sensitivity analyses for both primary and secondary endpoints are described in [Table AMAJ.6.5](#) and [Table AMAJ.6.6](#).

6.12. Health Outcomes/Quality-of-Life Analyses

Analyses of PSS, Global Assessment Dermatology Life Quality Index (DLQI), Patients Global Assessment of Psoriasis (PatGA), Work Productivity and Activity Impairment-Psoriasis (WPAI-PSO), TSQM, EQ-5D-5L + Bolt on, QIDS-SR16 and SF-36 health outcomes are described in [Table AMAJ.6.5](#) and [Table AMAJ.6.6](#).

6.13. Bioanalytical and Pharmacokinetic/Pharmacodynamic Methods

Details of PK/pharmacodynamic (PD) analyses can be found in a separate PK/PD analysis plan.

6.14. Safety Analyses

The planned analyses of safety data will be performed with an intent to maintain consistency with compound level standard safety analyses. These standards are based on internal standards which were informed by Clinical Data Interchange Standards Consortium (CDISC) standards, regulatory guidance (for example, FDA Clinical Review Template), and cross-industry standardization efforts (for example, Pharmaceutical Users Software Exchange [PhUSE] white papers from the Standard Analyses and Code Sharing Working Group provided in the PhUSE Computational Science Deliverables Catalog [WWW]).

In general, safety evaluations will be based upon the following safety analysis populations with their associated study periods:

- Induction Safety Population
- All Active Treatment Safety Population

These analysis populations are fully defined in [Table AMAJ.6.1](#), while [Table AMAJ.6.2](#) describes the treatment groups, associated study periods and the comparisons for each analysis population.

Unless otherwise noted, Fisher's exact test will primarily be used to compare percentages, and odds ratios will be provided. Odds ratios will be created with mirikizumab treatment as the numerator, and placebo or secukinumab as the denominator.

Treatment differences in mean change for continuous measurements will be assessed using an ANCOVA model containing terms for treatment and the continuous covariate of baseline measurement. Type 3 sums of squares will be used. The significance of within-treatment group changes from baseline will be evaluated by testing whether the treatment group LS mean changes from baseline are different from zero using a t-statistic.

Not all displays described in this section will necessarily be included in the CSRs. Any display described and not provided in the CSR would be available upon request. Not all displays will necessarily be created as a "static" display. Some may be incorporated into interactive display tools instead of or in addition to a static display. Any display created interactively will be included in the CSR if deemed relevant to the discussion.

